2.0 Study Design

Summary of Reducing Adenoviral Patient-Infected Days (RAPID) Study

This is a double-masked, randomized pilot study to estimate planning parameters for a definitive large scale trial. In the pilot study, we will randomize 50 participants with adenoviral conjunctivitis confirmed by qPCR in 1:1 ratio to either one-time, in-office treatment with artificial tears or povidone iodine 5% (5% PVP-I). Follow-up care in both groups after treatment at baseline will be standard of care with single-use artificial tears 4 times-a-day until resolution of symptoms. The pilot study is funded by a NIH R-34 Planning Grant.

Key Eligibility Criteria

1. Ability to provide written informed consent;
2. At least 18 years of age, male or female, of any race;
3. Self-reported onset of symptoms in first affected eye \leq 4 days of presentation;
4. Adeno-viral conjunctivitis in study eye confirmed by RPS AdenoPlus™;
5. Females capable of becoming pregnant must have negative urine pregnancy testing.

Key Exclusion Criteria

1. History of hypersensitivity to iodine or Betadine™ or thyroid disease;
2. History of herpetic eye disease;
3. Ocular surgery in study eye within the past 3 months;
4. Presence of skin vesicles, corneal subepithelial infiltrates, corneal dendrites, traumatic corneal abrasion, corneal ulcer, foreign body, or conjunctival membrane/pseudomembranes, or anterior chamber cell or inflammation in study eye on slit lamp examination;
5. Females who are pregnant or lactating or have positive urine pregnancy test.

Study Visits

Screening/Baseline visit includes completion of RAPID symptom survey, a comprehensive eye examination including visual acuity, SLE, fluorescein staining, RPS AdenoPlus™ and tear sampling for molecular diagnosis.

Eligible patients are randomized to receive one-time, in-office dose of 5% PVP-I or artificial tears at baseline and complete 5 f/up visits (1-2, 4, 7, 14 and 21 days). Tear samples for molecular diagnosis are taken at each f/up visit and AdenoPlus™ testing continues til 2 consecutive negative tests.

Ineligible patients will receive standard of care outside of the RAPID study.

Unmasked clinician/technician administers randomized treatment.

Masked clinician/technician completes all follow-up visits.

2.1 Specific Aims

There are no published clinical trials evaluating the efficacy of one-time, in-office administration of 5% PVP-I against a control group. A definitive trial has the potential to alter clinical practice patterns whether 5% PVP-I is shown to be efficacious or not. Our long-term goal is to conduct a definitive, randomized clinical trial (under an NEI UG1 grant award) that evaluates whether or not a single, in-office application of 5% PVP-I is more effective than artificial tears alone at reducing viral load and improving symptoms in patients with Ad-Cs. To optimize the design of such a large-scale clinical trial, we are conducting this R34-planning study. We will use this planning study to address three specific aims that will yield information that is critical to the successful design of the UG1 RCT.

Aim 1: Evaluate the performance of the RPS AdenoPlus™ detector in determining study eligibility by comparing the RPS AdenoPlus™ case positive eyes in patients presenting with conjunctivitis to molecular diagnosis such as PCR testing.

While molecular diagnosis such as PCR is the gold standard for adenovirus detection, PCR is performed off-site and delays diagnosis by 24-48 hours. The inaccuracy of clinical diagnosis of Ad-Cs based on patient signs and symptoms has been extensively documented. We will use the RPS AdenoPlus™, a rapid in-office detection system, to screen for Ad-Cs and will adjust sample size of the future UG1-funded study to reflect the false-positive rate associated with this device.

Aim 2: Assess patient visit completion, change in patient-reported symptoms and PCR-determined viral load and masking during the 21 day follow-up period.

We will assess participants over six visits, baseline (treatment randomization) and follow-up at 1-2, 4-5, 7, 14 and 21 days. We will quantify rates of visit completion and changes in participant-reported symptoms and viral load by qPCR at these time-points. These data will be used to determine the necessity and feasibility of a shorter/longer follow-up period in the UG1 clinical trial. We will also assess participant-reported eye discomfort due to treatment using a 10 point visual analog scale to assess participant tolerance of 5% PVP-I. Masking of participants will be assessed at baseline and at visit day 4-5. Success of clinician masking will be assessed at baseline and day 14.

Aim 3: Correlate changes in PCR-determined viral load with changes in clinical signs and symptoms.

Improvement in clinical signs and symptoms is the most important outcome from the participant's perspective and a prerequisite for wide adoption of 5% PVP-I as Ad-Cs therapy. The data collected in this planning study at baseline, 1-2, 4-5, 7, 14 and 21 days will be used to start probing this relationship and to identify the key variables that could be more directly focused on and addressed fully in the larger UG1-funded Ad-Cs clinical trial.

These Aims will provide key planning parameters for the preparation of a Manual of Procedures for a national, multi-site clinical trial to test definitively whether or not a

single, in-office treatment of 5% PVP-I is more effective than artificial tears at reducing viral load and improving symptoms in participants with Ad-Cs. 2.2 Study Organization Steering Committee members include Clinical Center PI's and Coordinating Center Director:

1. [name] O.D., FAAO Illinois College of Optometry
2. [name] O.D., Ph.D, Ohio State University
3. [name] O.D., Northeastern State University
4. [name] O.D., FAAO, Washington University School of Medicine
5. [name] O.D., University of Illinois
6. [name] O.D., M.S., (Study Chair), University of Alabama at Birmingham
7. [name] Ph.D., (Director) Coordinating Center, Washington University School of Medicine

The Steering Committee will meet weekly by teleconference as it has done since the summer of 2012, and in person 1-2 months within study funding and at 12-14 months to develop the UG1 study protocol. The Steering Committee will be responsible for monitoring study progress semi-annually, completing planning studies, designing the UG1 collaborative study protocol, preparation of the Manual of Procedures, and UG1 collaborative studies grant application.

2.3 Schedule of Visits, Tests and Measures

Procedure	Screening/Baseline Exam Pts. \geq 18 yrs. presenting w pink eye Unmasked or Masked Clinician/Technician	Follow-up Exam Randomized Pts. at 1-2, 4-5, 7, 14, 21 days Masked Clinician or Masked Technician
Pt. washes hands upon entering exam rm.	X	X
Written Informed Consent	X	n/a
Examiner-Administered Symptom Survey	X	X
Medical and Ocular History	X	X
Snellen Visual Acuity Pinhole if VA worse than 20/20	X	X
Slit Lamp Examination	X	X
Grading of Ocular Signs	X	X
Subepithelial Infiltrate Check	X	X
Lymph Node Palpation	X	X
Pregnancy testing for women of childbearing age	X	n/a
AdenoPlus™ Testing and photograph RPS test display	X	Continue RPS testing until 2 negative results
Tear sample for molecular diagnosis	X	X
Fluorescein Grading	X	X
Clinician Prediction of Cause of Pink Eye	X	n/a
	Randomization of Study Eye of Eligible Patients	
Randomization to artificial tears or 5% PVP-I (Betadine™5%)	Unmasked Clinician/Technician Administers Randomized treatment	n/a
Repeat Fluorescein Grading	X	n/a
Pt. receives artificial tears for 21 days	X	X
Staff gives gift card to pt. & completes check voucher for \$20	n/a	X
Complete disinfection protocol	X	X

2.4 Recruitment of Patients with “Pink Eye”

(Appendix 2-A “Recruitment Screening Script”)

Participants who present with “pink eye” will be ushered directly to a designated “red eye” examination room. If a designated room is not available, the patient will be ushered to a designated “red eye” chair in the waiting area. Magazines adjacent to chair will be disposed of afterwards in a red biohazard bag. The chair surface will be disinfected with hypochlorite bleach or cavicide wipes.

Participants, who are ≥ 18 years of age and report symptom in the first affected eye onset ≤ 4 days, will be informed of the study by Clinical Center personnel and asked if they would be interested in learning more. Patients expressing interest in the study will discuss study participation with a study certified clinician/coordinator in a specially designated “Red Eye” examination room. (**Appendix 2-B, “Sample Consent Form”**)

Upon entering the “red eye” examination room, the study certified clinician/technician will request the patient to wash their hands. The clinician/technician will turn on the water and dispense soap. The patient dries hands with paper and disposes of paper towels in red biohazard bag.

The study certified clinician/coordinator will explain the study to the patient, answer all questions and provide a brochure (Appendix 2-C “RAPID Recruitment Brochure”). The brochure will include information about adenoviral conjunctivitis (public health impact and proper hygiene to reduce infection and diagnosis) and describe the RAPID study and provide Clinical Center contact information.

Patients who decline study participation will be treated according to the standard of care with artificial tears as recommended by the American Academy of Optometry and American Ophthalmology Academy. Patients who decline participation will not be assigned a study ID code. The patient EXITS the study and no more questions need to be completed. The visit date and gender of patients who decline participation will be maintained on a screening log. No other data is retrieved on patients who decline participation.

Patients who agree to study participation and will sign two copies of the consent form and will be assigned a study ID code. The clinic files one in a red folder indicating biohazard. The other copy is given to the patient along with the pen used to sign.

All research data are identified only by study ID code. No personal identifying data are collected as research data. All subsequent study forms are completed by study personnel to reduce risk of infection transmission.

2.5 Recruitment, Consent and Tear Sampling in Control Patients

Approximately 50 normal, healthy adult controls (age ≥ 18) at each clinic will be invited to provide a one-time tear sample for immunoassay and molecular diagnosis to describe ocular microbiome in the normal eye. Control eyes will provide a baseline against which to compare microbiome in eyes that present with “pink eye” infected with

adenovirus and/or other infectious agents including co-infection by bacteria. A high prevalence of adenovirus co-infection with bacteria causing conjunctivitis could favor the use of a broad spectrum anti-microbial agent such as betadine rather than an anti-viral agent.

A study certified clinician/technician will explain the study to healthy adults and answer all questions. Individuals who agree to possible participation will sign a copy of a consent form for healthy, adult volunteers. They will be assigned a study ID code and be asked to complete a form asking age, gender, race/ethnicity and if they have taken prescription medications for an ocular condition in the last 2 months. Those who answer “yes” are excluded. No other data will be collected from controls. There is no follow-up beyond the day of presentation and there is no payment for participation. The control volunteer receives a photocopy of the consent form and the original is filed at the clinic in a HIPAA compliant office.

A study certified clinician/technician will instill a drop of 0.5% of proparacaine anesthetic to numb one eye. After 5 minutes, a tear sample will be taken from the lower lid with an RPS flock for immunoassay and swab for molecular diagnosis.

Potential adult controls who decline study participation will be treated according to the original purpose of their visit. No patients will be specifically called in to serve as an ocular control.

2.6 Screening Examination for Patients with “Pink Eye” (Appendix 2-D “Screening/Baseline Form”)

Re-Confirm age ≥ 18 years

Study certified personnel will confirm patient age (≥ 18). If age is less than 18, the patient EXITS the study, the examination stops here and no more questions need to be completed.

Ocular Symptom Survey

Study certified personnel will read ocular symptom questions in quotes “word-for-word”. Duration of symptoms (again) in first affected eye (≤ 4 days) will be asked again as confirmation. If symptom duration is greater than 4 days, the patient is ineligible but will complete the screening examination, but will not complete the Screening/Baseline Form for eligible patients.

History and Eye Examination

Study certified personnel will complete:

1. Case history to determine history of allergy to iodine or Betadine, eye surgery within 3 months, thyroid disease, herpes related eye infection, pregnancy status;
2. Snellen visual acuity-corrected or uncorrected, pinhole if $< 20/20$;
3. Lymph node palpation;
4. Skin vesicles;
5. Slit lamp examination;

- a. grading of eyelid edema
 - b. eye lid matting
 - c. tearing
 - d. purulent discharge
 - e. bulbar conjunctival edema
 - f. bulbar redness
 - g. hemorrhage
 - h. conjunctival papillary response
 - i. conjunctival follicular response
 - j. conjunctival membrane
 - k. corneal subepithelial infiltrates
 - l. corneal ulcer
 - m. presence of foreign body
 - n. corneal dendrites
 - o. anterior chamber flare
 - p. anterior chamber cell
6. AdenoPlus™ testing;
 7. Tear Sample for molecular diagnosis
 8. Fluorescein staining.
 9. Urine pregnancy test for females of childbearing age who are eligible

2.7 RPS AdenoPlus™ and Tear Samples for Molecular Diagnosis

All patients \geq 18 years of age who present with “pink eye” and consent to study participation will be tested with AdenoPlus™ (Rapid Pathogen Screening, Sarasota FL). After a 5 minute interval to replenish tears, a tear sample will be taken for molecular diagnosis. The first affected eye will be tested and defined as the “study eye”.

If both eyes are clinically eligible and both eyes developed symptoms at the same time, the study eye will be selected randomly by coin toss. Data from both eligible and ineligible patients will enable exploration of the relationship between symptoms, clinical signs and Ad-Cs.

2.8 RPS AdenoPlus™ Testing

1. If patient is wearing contact lens in study eye, remove CL's;
2. Place disposable Chux pad on the counter;
3. Instill 1 drop of proparacaine 0.5% in study eye;
4. Instruct the patient to look up and expose the inferior palpebral conjunctiva by lowering the eyelid;
5. Dab and drag the sampling fleece along the inferior palpebral conjunctiva 8 times; begin temporally moving nasally with each dab/drag movement;
6. Rest fleece against nasal palpebral conjunctiva for 5 additional seconds;
7. Assemble the test by firmly placing the sample collector into the test cassette body;
8. Remove the protective cap from the test cassette and place the absorbent tip into the buffer for 20 seconds;

9. Remove the tip from the buffer, replace the protective cap and lay horizontally on a flat surface for 10 minutes, but not more than 1 hour; Set timer for 10 minutes and record time in military time.
10. Write ID & date on cassette next to display window, photograph cassette with standard color chip with smart phone within 4 hours under ambient exam room lighting.

2.9 Tear Sample for Molecular Diagnosis

1. 5 minutes after AdenoPlus sampling, take tear sample with flocked swab for molecular diagnosis.
2. Remove flocked-swab and vial of Universal Viral Transport Medium from sterile packaging.
3. Confirm that it has been 5 min since 1 drop of proparacaine 0.5% was instilled in study eye.

Tear Sample Collection

[figure not shown]
4. Pull down lower lid and hold swab approximately parallel to conjunctival fornix, with handle of swab pointing temporally.
5. Place swab on nasal palpebral conjunctiva and pull swab across palpebral conjunctiva until it reaches temporal angle.
6. Rotate the swab 180° and then slide swab back across the palpebral conjunctiva going from temporal to nasal side.
7. Hold the swab flat along the nasal palpebral conjunctival for 5 seconds.

Storage

8. Open vial and place swab in vial so that flocks are immersed in the medium.
9. Snap off the excess handle by pulling the swab against the vial at the scored line.
10. Screw cap tightly.

Labeling

11. Record date & participant ID# on label. Affix bar code label. Do not enter name or date of birth.
12. Sample can be stored at room temperature until transport to -20 or -80 degree freezer within 4 hours of collection.

10 minutes after RPS AdenoPlus test, Interpret RPS AdenoPlus™

No Blue Line – Invalid result

If a blue line is not visible, then the test is not valid. The test must be repeated.

Only Blue Line – Negative

If there is only a blue line, then AdenoPlus™ is negative for Ad-Cs. Complete the eye examination, fluorescein staining grading and manage the patient according to the standard of care with artificial tears. Patient EXITS the study at this point and no additional questions need to be completed.

Red Line (Solid or partial) – Positive

If there is partial or solid red line in addition to the blue line, then AdenoPlus™ is positive for Ad-Cs.

Pregnancy Testing

Female patients who are clinically eligible and RPS positive must complete urine pregnancy test to rule out pregnancy.

Negative pregnancy test: If the pregnancy test is negative, and the female patient is clinically eligible and RPS positive, will complete the “Randomization” Form for eligible patients, qPCR and treatment randomization.

Positive pregnancy test: if the pregnancy test is positive, the female patient is ineligible. Complete the eye examination, fluorescein staining grading and manage the patient according to the standard of care with artificial tears. Patient EXITS the study at this point and no additional questions need to be completed.

Shipping of Tear Sample to Washington University

- Sample can be stored at room temperature until transport to -40 or -80 degree freezer within 4 hours of collection.
- All specimens for a participant should be sent in the same shipment using the shipping carton provided by the Coordinating Center with a shipping manifest. Follow shipping instructions for biohazard specimens for molecular testing at your institution.

2.10 Randomization (Appendix 2-F, Randomization Form)

Participants who meet eligibility criteria including an AdenoPlus positive test are eligible for randomization. Randomization will be performed using a coded, sequentially numbered sealed envelope kept in the examination room. Randomization plan will be stratified by clinic and use a permuted block design with small random sized blocks. Treating (UNMASKED) clinician or technician administers the randomized treatment packet which includes the randomization assignment and one bottle of treatment-artificial tears or 5% PVP-I.

Treatment Protocol

Participant will not be informed of the treatment assignment. If the fellow eye presents with symptoms of Ad-Cs, it will be treated according to the standard of care with artificial tears.

Treating (UNMASKED) clinician or technician opens the randomization packet, completes randomization form and administers the randomized treatment - one bottle of either -artificial tears or 5% PVP-I.

1. Instill 1 drop of proparacaine 0.5% in study eye.
2. Open randomization package.
3. Instill 4 to 5 drops of assigned treatment (either artificial tears or 5% Betadine™) in inferior fornix.
4. Instruct participant to gently close his or her eyes and set timer for 2 minutes.
5. Gently place gloved finger on closed treated eye.
6. Ask participant to look up/down and left/right.
7. With the participant's eye closed, use 2x2 gauze moistened with assigned treatment and dab along the eyelid margins.
8. Make a dam with Kleenex around treated eye.
9. Lavage the ocular tissues with sterile saline irrigation solution.
10. Take another 2x2 gauze moistened with sterile saline and dab along lid margins to remove all residual treatment solution and dispose in a red bag.
11. Dispense in each eye 8-10 preservative-free, single use artificial tears q.i.d. for 2 days.

2.11 Discharge Instructions (Appendix 2-G, Discharge Instructions)

Upon completion of the Baseline Visit, the participant will receive "Discharge Instructions" for eye care and prevention of adenovirus transmission.

2.12 Follow-Up Visits (Appendix 2-H, Follow-up Visit Form)

The **masked** clinician or **masked** technician, not the treating clinician/technician will perform follow-up examinations.

Five follow-up visits should be scheduled \pm 3 days of the target date and at least 4 days apart as follows:

1. 1-2 days (\pm 1);
2. 4-5 days (\pm 1);
3. 7 days (\pm 3);
4. 14 days (\pm 3);
5. 21 days (\pm 3). If symptoms have not resolved by day 21, clinician will continue to follow the participant for further assessment.

The masked clinician/technician completes follow-up visits as follows:

1. Ocular symptom survey;
2. Visual acuity;
3. Lymph Node Palpation;
4. Slit lamp examination;
5. Tear sampling for qPCR.

Conjunctival swabs for qPCR will be placed in a cooler immediately and stored in a -40 or -80 freezer. When the participant has completed all follow-up visits, all swabs from baseline and follow-up visits will be batched and sent to Washington University ([name]) for storage in a -80 freezer. When samples for 6-10 participants (6 samples per participant) have been received, the samples will be walked to the Washington University pediatrics virology laboratory ([name]) for DNA extraction and molecular diagnosis including qPCR with

the Focus Diagnostics cycler. Samples of DNA and unprocessed samples will be returned to the [name] lab for long-term storage.

6. RPS testing of study eye until 2 consecutive negative test results. Photograph RPS display window labeled with ID/date along w standard color chip in ambient exam room lighting. RPS is done after tear sampling for molecular diagnosis because molecular diagnosis provides quantitative measure of viral burden and is the primary outcome of the study. Repeat RPS testing is done to determine consistency of RPS results and to identify sensitivity compared to molecular diagnosis.

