2.21 Statistical Analysis Plan: Primary Efficacy Outcome

RAPID is a National Eye Institute funded R-34 planning study. The target sample size of 40 (20 per group) is selected assuming a large effect size of 0.80, power = 0.80, and a nominal two-sided alpha of 0.05. To decrease the probability of failing to reject a null hypothesis, there is no correction for multiple comparisons.

The primary efficacy outcome is reduction from peak viral load defined as the percent reduction of DNA copies per ml from the participant's peak viral load. The Data and Safety Monitoring Committee approved a modified intention to treat analyses (mITT) to test efficacy outcomes in participants with detectable viral load by qPCR at baseline. The mITT analysis should not bias efficacy results because samples for qPCR were taken from all screened patients prior to randomization and qPCR results were never disclosed to participants or study personnel. Safety is assessed using all randomized participants per intention-to-treat.

The primary outcome and other quantitative variables including symptoms and signs will be analyzed using nonparametric Wilcoxon rank order tests. The exact p-value will be calculated by a computational network algorithm (Mehta and Patel, 1983) given that asymptotic results assuming a normal distribution cannot be assumed with small sample sizes. Nominal variables will be analyzed using Fisher's exact test. Treatment "effect size" (PVP-I mean minus AT mean divided by their standard deviation) will be calculated for the primary outcome to supplement p-values. Cohen has classified effect sizes of 0.2 as "small", 0.5 as "medium" and 0.8 as "large". (REF: Cohen J. Statistical Power Analysis for the Behavioural Sciences. 2nd ed. Hillsdale, NJ: Erlbaum Associates; 1988.)

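### Does reversing the order of the AdenoPlus test and the qPCR swab between baseline and follow-up undermine the viral-load outcome or the AdenoPlus accuracy estimates?

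*Combined protocol and SAP*

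**What the plan says.** Baseline. Section 2.7 has every consenting patient tested with AdenoPlus first, and then: "After a 5 minute interval to replenish tears, a tear sample will be taken for molecular diagnosis". Section 2.9 repeats this: "5 minutes after AdenoPlus sampling, take tear sample with flocked swab for molecular diagnosis". The AdenoPlus result decides entry; section 2.10 states "Participants who meet eligibility criteria including an AdenoPlus positive test are eligible for randomization". For healthy controls, section 2.5 also lists the AdenoPlus sample before the swab: "a tear sample will be taken from the lower lid with an RPS flock for immunoassay and swab for molecular diagnosis".

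Follow-up. Section 2.12 puts the swab first and gives its reason: "RPS is done after tear sampling for molecular diagnosis because molecular diagnosis provides quantitative measure of viral burden and is the primary outcome". It goes on: "Repeat RPS testing is done to determine consistency of RPS results and to identify sensitivity compared to molecular diagnosis". It states no interval between swab and AdenoPlus. Appendix 2-H, the follow-up form, is not in the text available.

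Analysis. Section 2.21 defines the primary efficacy outcome as "reduction from peak viral load defined as the percent reduction of DNA copies per ml from the participant's peak viral load", and uses a modified intention-to-treat set to "test efficacy outcomes in participants with detectable viral load by qPCR at baseline". It is titled for the primary efficacy outcome. It contains no AdenoPlus-versus-qPCR analysis and does not mention sampling order. Aim 1 (section 2.1) compares AdenoPlus with PCR in patients who present with conjunctivitis, and uses the false-positive rate to adjust the size of the later trial.

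**The concern.** AdenoPlus sampling is not a light touch. Section 2.8 has the fleece dabbed and dragged eight times along the lower palpebral conjunctiva and then rested there for five seconds. The swab in section 2.9 crosses the same surface. If the first contact removes virus, the second sample reads low. At baseline that is the qPCR swab; at follow-up it is AdenoPlus.

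Four quantities could be touched:

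- the size of the reduction from peak, because baseline and follow-up swabs are collected under different conditions;
- entry to the modified intention-to-treat set, which needs a detectable baseline qPCR;
- the AdenoPlus false-positive rate, because a virus-positive eye missed by a weakened baseline swab would be counted as a false positive;
- AdenoPlus sensitivity at follow-up, because a weakened second sample counts against the device.

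The last two errors differ in kind, so a single accuracy estimate pooled over all visits would mix them. The purpose of this pilot is to supply planning figures, so how they were measured matters.

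**Working it through.** **1. Can the order favour an arm?** The baseline swab is collected before allocation, and every follow-up swab is the first contact in both arms. Any loss is therefore common to both arms. If there is no treatment effect, the arms remain exchangeable and the rank test keeps its level. Selection on detectable baseline qPCR also rests on a pre-randomization sample.

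**2. Effect on the recorded reduction.** The documents give no loss, so let f be the assumed share lost in the second sample. If baseline is the peak and R is the true reduction, the recorded reduction is 1 − (1 − R)/(1 − f).

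| True R | f = 0.10 | f = 0.25 | f = 0.50 |
|---|---|---|---|
| 50% | 44% | 33% | 0% |
| 90% | 89% | 87% | 80% |
| 99% | 98.9% | 98.7% | 98.0% |

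For example, with R = 0.90 and f = 0.50: 1 − 0.10/0.50 = 0.80. For constant f this expression rises with R, so while baseline is everyone's peak the ranks, and hence the Wilcoxon test, do not change. When the peak is itself a follow-up sample, the order difference drops out of the reduction.

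**3. When the peak can move.** Assumed model: log10 baseline load N(6, 1); change at day 1-2 N(−0.2, 0.6); change at day 4-5 N(−0.7, 0.7), independent. Put s = log10(1 − f) = 0, −0.097, −0.301 for f = 0, 0.2, 0.5. Then

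P(peak at follow-up) = 1 − Φ((0.2 + s)/0.6) × Φ((0.7 + s)/0.7) = 0.469, 0.542, 0.690.

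Simulation: 20 per arm, 4,000 runs, percent reduction at day 4-5 from the highest of three samples, asymptotic Wilcoxon test, two-sided 0.05. Section 2.21 names no time point, so day 4-5 is a choice made here.

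| Quantity | f = 0 | f = 0.2 | f = 0.5 |
|---|---|---|---|
| Rejection with no arm difference | 0.050 | 0.053 | 0.050 |
| Median recorded reduction | 84.5% | 82.1% | 77.0% |
| Power, 0.5 log10 effect at both visits | 0.36 | 0.32 | 0.22 |
| Power, effect at day 4-5 only | 0.53 | 0.51 | 0.48 |

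The fall from 0.36 to 0.22 depends on the slow assumed decline, which leaves about half the peaks at follow-up. Repeating the run (3,000 runs, effect at both visits) with faster declines:

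| Mean change, day 1-2 and day 4-5 | f = 0 | f = 0.2 | f = 0.5 |
|---|---|---|---|
| −0.7 and −2.0 | 0.50 | 0.48 | 0.43 |
| −1.2 and −2.0 | 0.56 | 0.56 | 0.56 |

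At 50% loss the fall in power is therefore 0.14, 0.07 or nil, according to an input that the documents do not give.

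**4. Analysis-set entry and false positives.** Under the same N(6, 1) baseline, with an assumed qPCR limit of 10^4 (2 SD below the mean), order turns a detectable sample undetectable with probability Φ(−2 + |s|) − Φ(−2) = 0.6 points at 20% loss and 2.2 points at 50%. With a limit of 10^3 (3 SD below) it is 0.05 and 0.2 points. One such case among 50 AdenoPlus-positive eyes moves the false-positive share by 1/50 = 2 points. At 2.2 points the expected number is about 50 × 0.022 = 1.1 cases; at 0.6 points it is 0.3.

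**5. AdenoPlus taken second at follow-up.** If loads have SD 1 log10, the largest possible fall in positivity is Φ(|s|/2) − Φ(−|s|/2) = 3.9 points at 20% loss and 12.0 points at 50%. That maximum needs the device limit to lie near the middle of the load distribution. With the limit 2 SD below the mean the fall is 0.6 and 2.2 points.

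**6. Is pooling planned?** Aim 1 is worded for presenting patients, so its pairs are baseline pairs in one order. No section proposes combining them with follow-up pairs. Only the follow-up sensitivity purpose in section 2.12 is left without an analysis description.

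**The case for a change.** The strongest case for acting is that the protocol itself treats order as relevant. It puts the swab first at follow-up to protect the primary outcome and requires a wait at baseline for tears to replenish. The reason given in section 2.12 would apply to the baseline swab as well, and the documents never say why baseline differs. In a planning study, the argument runs, a limitation sentence, a split table and clearer wording in sections 2.9 and 2.12 cost almost nothing. Follow-up AdenoPlus results are also selected: they exist only in eyes positive at entry, and testing stops after two consecutive negatives. That alone argues against pooling, even with no carry-over.

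Much of this stands as advice on reporting. Follow-up sensitivity should be read with its sampling order and its selection in view, and kept apart from the baseline comparison. It does not show that the plan goes wrong. At baseline the first sample goes to the test that decides entry and that Aim 1 evaluates; swabbing first would move any loss onto that test. Splitting the tables cannot separate order from falling viral load, and it widens the intervals. Section 2.9 sits between the screening examination and randomization and contains screening exit rules, so its five-minute instruction reads as a baseline instruction. The interval at follow-up may be on the form that is not available.

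**Conclusion.** No change to the plan. The two orders are a fair trade-off: the first sample goes to the gating test at baseline and to the primary outcome at follow-up. The reversal is common to both arms and leaves the level of the primary test intact. If there is carry-over, it can make the recorded reductions look smaller (a median of 77.0% instead of 84.5% at an assumed 50% loss under slow decline) and can cost some power. The power cost runs from 0.14 to nothing across the declines tried, and every input is assumed. With no loss, nothing changes. The false-positive rate for the next trial already comes from baseline pairs, and under the same assumptions order would alter it by about one case in 50 at most. The SAP's silence on AdenoPlus accuracy reflects its scope, the primary efficacy outcome. What is left is a gap that analysts fill sensibly when reporting: state the sampling order beside the follow-up sensitivity, and mention the difference when interpreting the size of reductions from peak.
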